Aim 3 (A3). Evaluate the impact of the staff intervention on resident falls, accidents and injuries and on quality of life using a prospective experimental design that derives information from five sources: (1) resident interviews (2) staff informants (3) observational data (4) chart and (5) incident/accident report data.

Primary Hypothesis: The frequency of falls, accidents and injuries will decrease in the

intervention group, relative to the comparison group after implementation of the training intervention.

Secondary Hypotheses: 1. Resident quality-of-life as measured by affective state will improve in the intervention group, relative to the comparison group after implementation of the training intervention.

2. Resident behavior problems will decline in the intervention group, relative to the comparison group after implementation of the training intervention. Resident behaviors will mediate the relationship between the intervention and the falls/accidents/injuries outcome.

Trial design

This is a pragmatic, prospective, cluster randomized trial (facility level) design with three waves of data collection (baseline, 6- and 12-months) at 12 assisted living facilities in two New York regions. There will be three levels of clustering: facilities within regions, units within facilities and repeated measures on residents within units, with the regions fixed. On a rolling basis, six facilities will be selected at random and recruited in New York City and the nearby suburban counties (downstate region). Six facilities in the upstate New York region of Rochester will also be randomly selected. Three facilities in each region will be randomized to usual care or to the intervention on a 1:1 ratio. Facilities allocated to the usual care group will receive the intervention after completion of their 12 month data collection.

Methods: Participants, interventions and outcomes

Study setting

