Algorithms for conducting randomization that take into account clustering such as exists with geographical regions and rolling enrollment have been developed by the author. This method has yielded balanced groups for many studies. This randomization procedure will be carried out using a SAS macro after a facility completes the baseline interview. A random number from 0 to 1 will be used to determine the assignment group. The standard cut score will be set at 0.5 for the first n facilities from the same region. Facilities which receive a random number between 0 and 0.5 will be assigned to the usual care group and those with a random number greater than 0.5 will be assigned to the intervention group. The balance between the groups within each group will be carefully weighted after the total number of facilities from a group reaches a number greater than n. Before the randomization procedure, the number of facilities randomized to each arm for each region will be estimated using SAS macro programs. If more than the n facilities are randomized initially, the cut score for the next facility is equal to the ratio of the intervention group (n1) to the facilities already randomized (m) for that group (n1/m). For example, group A region provides eight facilities for randomization and the n is set to 5, the first five facilities (n) will be randomized to the standard cut score 0.5 (about half will go to the intervention and half to the usual care group). The sixth facility's randomization cut score is equal to the number of facilities in the intervention

group (n_1) divided by the total number of facilities randomized within that group (in this case, the denominator m is 5.) The seventh facility's cut score will be adjusted according to the previous six facilities, and so forth.

Concealment mechanism

The biostatistician who runs the randomization procedure passes the information directly to the intervention trainer who alerts the ALRs of their assignment. The principal investigator who oversees the data coordinating centre (DCC) at the Research Division, Hebrew Home at Riverdale (RD-HHAR) is the only other person made aware of the assignment.

Implementation

A biostatistician at the coordinating centre developed and runs the randomization procedure. Randomization occurs at the facility level. Research interviewers who enrol participants are blinded to randomization group.

Assignment of interventions: Blinding

Who will be blinded

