Statistical methods appropriate for clustered data will be used in the primary analysis to compare the groups with respect to the binary outcome. Generalized mixed effects models (MEMs) will be used to test the hypothesis that those assigned to the intervention will experience a significantly higher rate of fall/accident/injury reduction as contrasted with usual care. The outcome will be modeled as a function of intervention, time and their interaction and controlling for the baseline falls. To account for the clustered nature of the outcomes, the models will include random effects for facilities, units and subjects. The models will be fit using mixed effects logistic-regression as implemented in SAS Proc Glimmix. The appropriate covariance structure will be determined. The primary analysis will be supplemented with an exploration of the effect of baseline subject, facility and unit characteristics on the intervention effect. These results will inform generalizability of

intervention effects.

Analyses for secondary outcomes: The proposed secondary outcomes are affect, measured by the FTQ and the NIH PROMIS depression measure,^{61,62,63} and behavior. The reliability estimates of the outcomes are typically at least 0.90. Methods for analyses of treatment effects in pre-post clinical trials, in the context of missing data, have been compared.^{64,65,66,67,68,69} The primary proposed analyses will use MEMs, and a full information likelihood approach, with sensitivity analyses using generalized estimating equations (GEE).

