Statistical models: The primary endpoint analysis for comparison between the two groups with respect to various outcomes will be based on models for the outcome at 6 and 12 months as a function of the intervention condition, adjusting for the baseline value of the outcome, i.e. an ANCOVA-type MEM analysis with intervention as a factor with two levels and baseline value as a covariate. For multiple outcomes (e.g. NIH PROMIS and FTQ) MANCOVA-type MEMs will be used to simultaneously model the multiple outcome variables. An additional factor (domain) denoting the individual outcome variables will be included in the model together with interactions between domain (depression/affect measures) and intervention. A significant interaction term would indicate that the effect of the treatment is different for affect and depression; in that case two treatment effects will be estimated for each outcome. If the interaction is not significant a model with only main effects for depression/affect and treatment will be fit and the (common) treatment effect will be estimated from this model. In addition to significance testing, we will estimate the treatment effects with 95% CI. The MEMs allow modeling the correlation between the variables assessed on the same subject and that between subjects from the same units and facilities. Group differences in total scores will be examined using a linear mixed (fixed and random effects) model for effect estimation.

The use of SAS Proc MIXED will allow for the possible group heterogeneity in residual variances that may require modeling to satisfy model assumptions and improve model fit, and the modeling of the covariance structure. In secondary analyses, we will examine within subjects change over time. We did not perform power calculations for the secondary outcomes because the most

stringent power requirements are for the primary outcome. However, we will be able to detect relatively small effect sizes, given the sample size.

Examination of the exploratory potential mediating effects of behavior on the relationship between the R-REM intervention and the falls/injuries/accident outcome will be examined using mediation analyses. Although recent evidence from Monte Carlo studies support simple joint significance tests of the mediating path coefficients,^{70,71,72} also examined will be other formal tests of mediation effects.^{73,74}

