Based on prior experience with the outcomes, it is not expected that transformations will be necessary. Baseline variables will be examined by study arm; however, no p values will be provided, and covariates (other than baseline values) are not proposed for inclusion in the main analyses of treatment effects.

Examination of potential region differences: Data from regions (upstate and downstate) will be combined and each outcome (e.g., depression, affect) modeled as a function of two factors (i) intervention, a factor with 2 levels and (ii) region, a factor with 2 levels, and the interaction between (i) and (ii). MEMs will be used for each outcome, e.g., depression, and likelihood ratio tests (χ^2) used to test for significance of the interaction term. The study is not powered to detect meaningful regional differences in treatment effect; therefore we will use $\alpha=0.15$ as a criterion, and explore if regional differences are related to differences in intervention effects.

Interim analyses

There are no plans for interim analysis or predetermined stopping guidelines.

Methods for additional analyses (e.g. subgroup analyses)

Heterogeneity of Treatment Effects (HTE): Because there is interest in examining subgroups to determine for which individuals interventions may be effective, we will perform descriptive HTE with potential effect modifiers as interaction terms. HTE will be examined for subgroups, e.g., those with and without cognitive impairment.

Methods in analysis to handle protocol non-adherence and any statistical methods to handle missing data

Examination of baseline differences on key variables between completers and those lost-to-follow-up will be conducted to inform about the nature of the missing data. The ITT analyses performed using MEMs will permit all individuals with at least one post-baseline observation to be included.

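### Facilities are randomised within region, but no main model contains region; adding it as a fixed effect costs about one point of power and makes the sections agree

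*Combined protocol and SAP*

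**What the plan says.** Region is part of the design. The Trial design section nests facilities within regions, "with the regions fixed", and sets the allocation: "Three facilities in each region will be randomized to usual care or to the intervention on a 1:1 ratio". Sequence generation runs the allocation separately by region: "The standard cut score will be set at 0.5 for the first n facilities from the same region".

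Region is absent from every main model:

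- **Primary falls model** (Effect on likelihood of falls/injuries/accident reduction): "The outcome will be modeled as a function of intervention, time and their interaction and controlling for the baseline falls". For clustering, "the models will include random effects for facilities, units and subjects".
- **ANCOVA-type models** (Statistical models): "an ANCOVA-type MEM analysis with intervention as a factor with two levels and baseline value as a covariate".
- **Covariate rule** (just before Examination of potential region differences): "covariates (other than baseline values) are not proposed for inclusion in the main analyses of treatment effects".

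The only model that names region is the one under Examination of potential region differences. It has intervention, region and their interaction, and the interaction is tested at alpha 0.15. The plan says the study is not powered for this question, and the model does not supply the primary estimate.

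**The concern.** An analysis should normally reflect the strata used in the randomisation. Here the design section can be read as calling for a fixed region term, while the statistical section excludes one. Two competent analysts could fit different primary models.

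Two things follow if region is left out:

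- **Precision.** Any regional difference in fall rates goes into the between-facility variance, which only 12 facilities are available to estimate. With a 3:3 split in each region, the treatment contrast stays unbiased but the test becomes conservative.
- **Chance confounding.** If a region does not split 3:3, the arms can differ in their regional mix, and part of any regional gap enters the treatment contrast.

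The regions do differ in expected facility size (about 50 residents upstate and 125 downstate, Sample size section). That does not show that fall rates differ.

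**Working it through.** **1. The plan's own sample size.** The inputs, from the Sample size section, are p0 = 0.33, p1 = 0.2075, alpha 0.05, power 80%, reliability 0.95 and two follow-up waves with correlation 0.5 or 0.6. The stated inflation factor is 1 + 16(0.03) + 4(17)(0.015) = 2.5. Two-sided tests are specified in the statistical methods.

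Diggle formula at correlation 0.5, with mean rate 0.26875: (1.960√0.3931 + 0.842√0.3855)² × 1.5 / (2 × 0.1225²) = 153.3. Then 153.3 × 2.5 / 0.95 = 403.4.

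| Method | Correlation 0.5 | Correlation 0.6 | Stated |
|---|---|---|---|
| Diggle | 403.4 | 430.3 | 404 / 431 |
| GEE | 398.0 | 424.5 | 399 / 425 |

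The plan's figures reproduce.

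**2. Cost of the region term if region has no effect.** I keep the plan's variance and use a noncentral t test on facilities. Degrees of freedom go from 12 − 2 = 10 to 12 − 3 = 9, and the critical value goes from 2.228 to 2.262 (+1.5%).

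| Residents per arm | Correlation | Without region | With region |
|---|---|---|---|
| 525 | 0.6 | 80.1% | 79.2% |
| 445 | 0.6 | 73.4% | 72.4% |
| 525 | 0.5 | 82.6% | 81.6% |
| 445 | 0.5 | 76.1% | 75.1% |

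The cost is about 1 point. Put as sample size for 80% power at correlation 0.6, it is 523 against 537 residents per arm. These powers are below the plan's normal-theory values because there are only 12 facilities. That is a separate matter from region.

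**3. Gain if the regions differ, without baseline adjustment.** The gap is assumed (0, 3, 5 or 10 points), the split is 3:3, and 0.015 is taken as the within-region facility ICC. The variance of a facility mean is (0.015 + 0.015/5 + 0.72/87.5) × 0.1928 / 0.95 = 0.00532. The standard error of the arm difference is √(0.00532/3) = 0.0421, so the noncentrality is 0.1225/0.0421 = 2.91. A gap g adds g²/4 to the between-facility variance when region is omitted: 0.000625 at 5 points and 0.0025 at 10 points. Each setting used 200,000 simulated trials.

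**4. Gain with baseline falls as a covariate.** This is closer to the planned analysis. Resident-level binary data were simulated, 6,000 trials per setting (Monte Carlo standard error about 0.6 points near 72%). Each trial had six facilities of 50 and six of 125, five units each, the table's rates at each wave, wave correlation about 0.5, and ICCs of about 0.015 for facility plus 0.015 for unit. The gap was the same at all waves and there was no attrition. Follow-up facility means were adjusted for baseline with the pooled within-facility slope (0.40 to 0.43).

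Power without / with region:

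| Assumed gap | No baseline adjustment | Baseline, follow-up cluster effects unrelated to baseline | Baseline, cluster effects fully stable |
|---|---|---|---|
| 0 | 74.5 / 73.5% | 73 / 72% | 98 / 98% |
| 3 points | 73.0 / 73.7% | 71 / 70% | 98 / 97% |
| 5 points | 70.0 / 73.7% | 71 / 72% | 97 / 97% |
| 10 points | 56.5 / 73.6% | 67 / 72% | 95 / 98% |

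Without baseline adjustment, the false-positive rate when region is omitted falls to about 3.8% at a 5-point gap and below 2% at 10 points.

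**5. How often the split is 3:3.** Under Sequence generation, the first n facilities in a region go to intervention with probability 0.5. After that the probability is 1 − n1/m, where n1 of the m facilities already allocated are in the intervention arm. The text does not fix n for a region of six, so every value was enumerated exactly.

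| n | 3:3 in one region | 3:3 in both | Arms differ in regional mix by one third or more |
|---|---|---|---|
| 1 or 2 | 55% | 30% | 12% |
| 3 | 53% | 28% | 14% |
| 4 | 45% | 20% | 20% |
| 5 | 38% | 14% | 29% |
| 6 | 31% | 10% | 39% |

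A 4:2 split in one region with 2:4 in the other gives a mix difference of 4/6 − 2/6 = 1/3. The unadjusted contrast then moves by one third of the gap: 1.0, 1.7 or 3.3 points at gaps of 3, 5 or 10, against a planned difference of 12.25.

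**The case against.** The strongest reply is that nothing has been shown to be wrong.

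- **The conflict is an inference.** The phrase about fixed regions closes a sentence on clustering levels and names no model term. It may mean only that the two regions were chosen rather than sampled. Equally, the covariate rule may concern resident characteristics and not a design factor. This stands as a description of the ambiguity, but an ambiguity in the primary model still has to be settled before analysis.
- **The benefit is small under the planned model.** With baseline falls included, the region term changes power by at most about 1 point either way up to a 5-point gap, which is close to simulation error. This stands. The larger losses in the unadjusted column do not describe the planned analysis.
- **A 10-point gap is large relative to the plan's ICC.** It adds 0.0025/0.193 = 0.013 to the ICC, nearly the whole stated 0.015. If 0.015 already covers differences between regions, adding the gap on top overstates the loss. This is a fair limit on the last row.
- **The shifts from an uneven split are unadjusted.** With a baseline slope of 0.40 and a constant gap, they shrink by a factor of 0.60, to about 0.6, 1.0 and 2.0 points. The 39% figure is n = 6, where the balancing step never operates; n = 1 to 5 gives 12% to 29%. Both points stand.
- **A failure to reach 3:3 is an allocation problem.** That is true, and a region term is only a partial remedy. It does remove the part of the imbalance due to region.

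These points limit the size of the concern. They do not give a reason to leave the stratum out when including it costs about one point of power.

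**Conclusion.** The concern holds. As written, the statistical section omits the stratum within which facilities are randomised from the primary falls model and the ANCOVA-type models, and this sits badly with the Trial design section. Validity under a 3:3 split is not at risk, because the omission makes the test conservative.

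With baseline falls in the model, the loss of power is about 1 point or less up to a 5-point regional gap and about 3 to 5 points at 10 points. The cost of including region when it has no effect is about 1 point. An uneven split is likely under the stated allocation rule, and the region term then guards against chance confounding.

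The size rests on assumed gaps, since the documents give no fall rate by region, and on 0.015 being a within-region ICC. The calculations approximate the planned GLIMMIX model, and the plan states no denominator degrees-of-freedom method. If that method gives large degrees of freedom, the cost is close to zero. The change should be made, though the expected gain is modest.

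**What to change.** Add region (upstate or downstate) as a fixed effect to the primary GLIMMIX model for falls, accidents and injuries, and to the secondary mixed models under Statistical models. Amend the covariate sentence so that its exception covers region as well as baseline values; without that edit the new term would contradict it. Keep the intervention-by-region model as the separate exploratory analysis it already is.

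The cost is one model term, three short text edits and one of ten between-facility degrees of freedom. Adding region to a logistic model also changes slightly the conditional odds ratio being estimated, so the term should be specified before the outcome data are analysed.

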$\eta = \log(p_{ijk} / (1 - p_{ijk})) = \beta_0 + \beta_1 X_{ijk} + FU_{jk}$, where FU_{jk} is a random effect associated with facility and unit.

The formula for the sample size per group using the method of Diggle is:

$m^* = (z_{\alpha} \sqrt{2PQ} + z_{\beta} \sqrt{p_0 q_0 + p_1 q_1})^2 (1 + (n-1)\rho) / (n(p_1 - p_0)^2)$; and using the GEE method:

$m^* = \frac{(Z_{1-\alpha/2} + Z_{1-\beta})^2 (\pi_1 p_0 (1 - p_0) + \pi_0 p_1 (1 - p_1)) (1 + (n-1)\rho)}{2n\pi_0\pi_1(p_0 - p_1)^2}$. The formula below is adjusted with variance inflation factor (V_{if}) and reliability(R_{el}): $m = V_{if}m^* / R_{el}$ and

$$V_{if} = (1 + (n_e - 1)\rho_e)(1 + (n_s - 1)\rho_s n_e p_e / (1 + (n_e - 1)\rho_e))$$

where $n_s = 5$ is the average number of units in the facility, $\rho_s = 0.015$ is the ICC for facility, $n_e = 17$ is the average number of residents in the unit, $\rho_e = 0.03$ is the ICC for unit, and the reliability:

$$R_{el} = 0.95.$$

The following table assumes $\alpha = 0.05$, power $(1 - \beta) = 80\%$, $R = 0.95$ and $V_{if} = 2.5$ (With $n_e = 17$,

$ICC_{Unit} = 0.03$, $N_s = 5$, $ICC_{Facility} = 0.015$, the fall rate at follow-up: $p_0 = 33\%$ and $p_1 = 20.75\%$). Two

scenarios for ρ (the average correlation of the outcomes over waves) were posited:

Group	Fall rate P(y=1)				Diggle Method		GEE Method	
	Baseline Rate	6 Month	12 Month	Combined 6M & 12M	M ($\rho = 0.5$)	M ($\rho = 0.6$)	M ($\rho = 0.5$)	M ($\rho = 0.6$)
Intervention	37%	22%	19.5%	20.75%	404	431	399	425
Usual Care	37%	34%	32%	33%	404	431	399	425

As shown, with 525 per group, power is adequate for intent-to-treat (ITT) analyses, including all respondents. Because randomization is at the facility rather than individual level, there is the potential for imbalance on baseline variables and missing covariate data. Assuming attrition of

15% at wave 1, it is estimated that 445 per group will have at least baseline and one additional wave of data included, using the EM missing data algorithm; thus, power is adequate to detect the posited difference in fall reduction of about 12% even with attrition.

Recruitment

All residents are approached and invited to participate. For those who do not wish to be interviewed, a different or the same interviewer approaches again at another time that may be more amenable to the resident. All resident questions are addressed and interviews occur at a time and place preferred by the resident.

Assignment of interventions: allocation

Sequence generation

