Demographic variables of interest include age, race, educational attainment, and length of stay in the facility. Medical diagnoses, medications, activities of daily living, cognitive impairment and mental health data will be extracted from the Assisted Living Residence Medical Evaluation form. Diagnosis information will be integrated into a comorbidity index, in order to adjust for burden of chronic illnesses. Interrater reliability will be examined on a random subset of charts. In addition, physical function, including history of falls in the past 3 months, frequency of falls, resulting injuries and open-ended comments and behavioral issues data will be extracted from the Assisted Living Resident Evaluation Form that is completed at admission. The resident Individual Service Plan will be reviewed for reports of occurrences of R-REM, falls, incidents and injuries and other covariate information that develop from three months prior to baseline through the study end.

5. Accident/ Incident Reports

The New York State Department of Health mandates electronic transfer of accident and incident reports to regional offices as part of licensing standards for ALRs statewide. Federal regulations require the reporting of alleged violations of abuse, mistreatment and neglect, including injuries of unknown origin to the facility administrator and in accordance with state law. The reports will be reviewed for potential incidents of R-REM and falls. Data will be collected from three months prior to the study through the end of data collection. Each incident report reviewed for resident falls/ accidents/ injuries may also contain evidence of R-REM.

6. Environmental Assessment

In addition, physical environment is assessed (direct assessment at local site): The modified Therapeutic Environment Screening Scale (TESS)⁵⁶ will be used by research staff to measure the physical environment. The TESS includes 12 domains: unit autonomy, exit control, maintenance, cleanliness, safety, lighting, space/seating, physical appearance/homeliness, access to outdoors, orientation and cuing, privacy, and noise, and a scale measuring quality. These data will

be collected for descriptive purposes, and for possible inclusion in hierarchical linear models.

Facility and unit characteristics will also be collected.

Plans to promote participant retention and complete follow-up

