Analyses for the primary hypothesis for the distal outcome: The primary analyses will examine, on an ITT basis, the differences between the usual care and intervention groups in the reduction of falls/accidents/injuries over time. Other approaches, e.g., the analysis of the “as treated” sample can result in biased estimates of the causal treatment effect due to compromised random assignment. Our primary approach to analyses is guided by our own experience,⁵⁷ and reviews.^{58,59} Depending on the level of missing data, analytic strategies (see below) can be used to address non-compliance, e.g.⁶⁰ Based on prior trials that we have coordinated, sampled from this population, 1 year attrition is between 30% and 40%; thus for 6-month data (projected attrition of 15%), the ITT analyses of all subjects will be feasible. Longitudinal analyses will include those with at least baseline and one follow-up. Sensitivity analysis will be performed using multiple imputation under different assumptions for missing data.

Because randomization is at the facility rather than individual level, imbalance may be observed on baseline variables. Preliminary analyses will be performed to determine whether the groups are balanced. Two-tailed tests of significance will be performed. Binomial tests are to be conducted on dichotomous variables, Poisson tests on nonbinomial (e.g., count) data, and *t* tests on ordinal data, adjusting standard errors for clustered data within facilities; *p* values are reported because the design does not permit randomization at the level of the individual.

Effect on likelihood of falls/injuries/accident reduction:

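### No planned analysis gives a case-mix-adjusted falls effect, although the plan collects covariates for adjustment and recognises that randomising 12 facilities may leave imbalance

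*Combined protocol and SAP*

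**What the plan says.** All sections are in the combined protocol and SAP.

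- **Main models.** Under Statistical models, "covariates (other than baseline values) are not proposed for inclusion in the main analyses of treatment effects". The same section shows that baseline values means the outcome's own baseline: "adjusting for the baseline value of the outcome, i.e. an ANCOVA-type MEM analysis with intervention as a factor with two levels". For falls, the section on the likelihood of falls/injuries/accident reduction says: "The outcome will be modeled as a function of intervention, time and their interaction and controlling for the baseline falls". Random effects for facility, unit and subject complete that model.
- **Covariate collection.** Under Chart data: "Diagnosis information will be integrated into a comorbidity index, in order to adjust for burden of chronic illnesses". The INCARE, described under Resident interview, is said to supply case-mix covariates, including cognition and ambulation.
- **Imbalance.** Under Sample size: "Because randomization is at the facility rather than individual level, there is the potential for imbalance on baseline variables and missing covariate data". The analysis section for the primary hypothesis repeats that imbalance is possible and plans a balance check, but ties no action to its result.
- **Baseline p values.** That analysis section says that p "values are reported because the design does not permit randomization at the level of the individual". Statistical models says that baseline variables will be examined by arm, "however, no p values will be provided".
- **Timing of chart data.** The Individual Service Plan is reviewed for "other covariate information that develop from three months prior to baseline through the study end".
- **Region.** The Trial design section describes regions as fixed and allocates within region. Region appears in a separate interaction analysis but is not listed in the falls model.

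**The concern.** The plan gathers data for adjustment, names the reason adjustment could help, and then specifies no analysis that adjusts. Other baseline characteristics enter only as possible effect modifiers, in missing-data methods under consideration, or, for the environment scale, for possible inclusion in hierarchical models. None of these yields an adjusted falls effect.

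Two things are at stake. First, with six facilities per arm, case-mix differences between facilities add variance to the arm difference, and resident-level covariates already in hand could remove some of it. Second, an acknowledged risk of imbalance, a balance check with no consequence and two conflicting statements on baseline p values leave the team without a rule if the arms do look different. A covariate set fixed in advance closes that gap.

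**Working it through.** **Step 1. The plan's own figures.** Inputs from Sample size: two-sided 5% level (two-tailed tests are stated in the analysis section), 80% power, follow-up fall rates 33% and 20.75% (difference 12.25 points), two follow-up waves, reliability 0.95, unit ICC 0.03 with 17 residents per unit, facility ICC 0.015 with 5 units.

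- Variance inflation: 1 + 16 × 0.03 = 1.48, and 1.48 × (1 + 4 × 0.015 × 17 / 1.48) = 2.50, as stated.
- Average p(1−p) = (0.33 × 0.67 + 0.2075 × 0.7925) / 2 = 0.1928.
- GEE formula, correlation 0.5: 2.8016² × 0.1928 × 1.5 / 0.1225² = 151.2; × 2.5 / 0.95 = 398.0, against 399 in the table. The other three entries also reproduce (403.4, 430.3 and 424.5 against 404, 431 and 425).

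The sample-size arithmetic is sound. The point concerns the analysis model.

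**Step 2. Yardstick.** 80% power for 12.25 points implies SE = 12.25 / (1.960 + 0.842) = 4.37 points.

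**Step 3. Contribution of case mix.** Let the facility share of a higher-risk group have standard deviation S, and let that group's any-fall risk be D higher. With six facilities per arm:

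SD of arm difference from mix = S × √(1/6 + 1/6) × D

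Neither S nor D is in the documents. The ranges below are assumptions.

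| S (points) | D (points) | SD from mix (points) | Share of 4.37² | Share of facility variance |
|---|---|---|---|---|
| 10 | 10 | 0.58 | 1.7% | 3% |
| 10 | 15 | 0.87 | 3.9% | 8% |
| 10 | 25 | 1.44 | 10.9% | 22% |
| 15 | 10 | 0.87 | 3.9% | 8% |
| 15 | 15 | 1.30 | 8.8% | 17% |
| 15 | 25 | 2.17 | 24.5% | 49% |

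The last column is (S × D)² / (0.015 × 0.1928), where √(0.015 × 0.1928) = 5.4 points is the facility SD implied by the plan's ICC. It is a plausibility check. The bottom row needs both extremes at once and has one covariate explaining about half of all between-facility variance.

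**Step 4. Translation.** If adjustment removed the mix component entirely, the SE would fall by a factor √(1 − share): about 1% in the top row and 13% in the bottom row. A 2-SD imbalance would move a single realised estimate by 1.15 to 4.33 points, which is 9 to 35% of 12.25. These are upper figures for each scenario, because baseline falls already removes an unknown part.

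**Step 5. Cross-check from the plan's ICC.** Facility effects as a whole give the arm difference an SD of √((2/6) × 0.015 × 0.1928) = 3.1 points. Every scenario lies below that ceiling.

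**The case against.** The strongest reply is that chance imbalance is already in the inference. The falls model controls for baseline falls and has facility and unit random effects, the 2.5 inflation factor allows for clustering, and allocation is by region. A prespecified model with only the baseline outcome is legitimate and guards against data-driven selection. This stands, and it fixes the nature of the harm. A reader might infer that the falls estimator is biased or the test invalid; under randomisation it is neither.

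Other stronger readings also lack support:

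- That the plan forbids adjustment. It only does not propose it, and only for the main analyses.
- That the plan expects imbalance. It says imbalance may occur.
- That the collected covariates are known strong predictors of falls. The documents link cognitive impairment, mobility and special-needs units to aggression or R-REM, and give no association with falls.
- That the team intends to choose covariates by baseline p values, or to adjust the main model for values recorded after training. No section says so.

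Two replies are weaker. Scarce facility degrees of freedom argue against facility-level covariates, but cognition, ambulation and comorbidity are resident-level, and region costs one term. Allocation by region does not make a region term redundant: the cut-score rule under Sequence generation does not force a 3:3 split. With six facilities it gives 3:3 with probability 31 to 55%, depending on a threshold n that is not stated for this trial.

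The objections to cost have force. Eligibility criteria excludes residents unable to respond from resident-level measures, so missing CAREDIAG scores may concentrate in the most impaired. In a logistic mixed model, added covariates also change the conditional odds ratio being estimated.

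**Conclusion.** The point holds as a gap in specification and a cheap gain in precision. The main models adjust only for the outcome's baseline, the stated purpose of the comorbidity index has no falls analysis behind it, and the two statements on baseline p values cannot both stand. The size is uncertain: about 0.6 to 2.2 points of SD in the arm difference, or 2 to 25% of the variance implied by 80% power. This rests wholly on the assumed spread of case mix and its assumed link to falls, ignores the within-region allocation, and does not net out baseline falls. Four of the six scenarios lie below 10%, so a modest gain is the more likely reading. The change is worth making because it is cheap and gives a fixed rule before outcome data are seen.

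**What to change.** 1. Replace the Statistical models sentence with a fixed covariate list for the falls and secondary models: region, baseline cognitive impairment, baseline ambulation and the comorbidity index. Add special-needs unit if it is recorded at baseline; the documents do not give its timing.
2. Use only values dated before the facility's randomisation. This is feasible, because Sequence generation places randomisation after the facility's baseline interview. Exclude service-plan or environment data recorded later, since Module 3 covers how staff can shape the social and physical environment.
3. Where resident-level scores are missing, use the chart cognition and ADL data, with a prespecified rule for remaining gaps.
4. Keep the model without these covariates as a named sensitivity analysis.
5. Report the falls effect also as a marginal risk difference, so that the adjusted and unadjusted models address the same quantity.
6. Reconcile the two statements on baseline p values by dropping the baseline significance tests and describing balance by arm and by facility.

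The cost is SAP wording and a few model terms. The listed resident-level variables are already to be collected. The plan should state the two downsides openly: missing cognitive scores may not be few or random, and the conditional odds ratio changes with the covariate set.
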